13.2. Assessment of Adverse Events (AEs)

All AEs must be assessed for Seriousness, Severity, and Relationship. All AEs, regardless of classification, must be comprehensively documented in the eCRF and on the SAE form, if applicable, and reported to BD. This includes AEs related to marketed study products. The following information about the event is to be reported on the AE eCRF:

- Seriousness, classified as: Non-Serious or Serious
- Severity, classified as:
 - Mild: Transient symptoms, easily tolerated, no interference with daily activities
 - Moderate: Marked symptoms, moderate interference with daily activities, tolerable
 - Severe: Considerable interference with daily activities, intolerable
- Relationship, to the study product or study procedures:
 - Not Related: Evidence suggests absolutely no possible causal relationship between the event and the investigational study device (or procedures).
 - Unlikely Related: Evidence suggests that other possible causes or contributing etiological factors may have caused the event other than the investigational study device (or procedures).
 - Possibly Related: Evidence suggests a causal relationship between the event and the investigational study device (or procedures) cannot be ruled out
 - Definitely Related: Evidence suggests a reasonable causal relationship between the event and the device (or procedures) is likely

In addition, the following should be recorded for each AE:

- Action(s) taken to remedy the AE, including change in study treatment or participation, or medical/surgical treatments
- Duration of the AE from onset through resolution, as applicable
- Cause (including suspected product/procedure and/or other cause)
- Outcome of the event, including resolution and sequelae, as applicable

13.3. Incidents

A Clinical Study Incident is defined as any problem or issue involving the study device(s), reference methods, associated procedures or equipment, or represents a product-related injury (or potential for injury) to study subjects or personnel as a result of execution of this protocol. Clinical Study Incidents may adversely (or potentially adversely) affect human safety, the integrity of the evaluation data, or the operation of devices or systems, and warrant prompt attention.

Incidents involving injury to study subjects will also be reported as Adverse Events (as explained above). Examples of Clinical Study Incidents that are not Adverse Events might be mislabeling or adulteration of the study device, device malfunctions, errors in the device instructions, damage to devices caused by shipping or handling or improper

storage, or injury to study personnel due to execution of the protocol. If appropriate, an Incident may also be documented and reported as a protocol deviation.

The Monitor should be contacted immediately when site becomes aware of or suspects any defective or malfunctioning product. This includes:

- BD Micro-Fine Plus 4mm 32G pen needles that are involved in Study Incidents,
- BD Micro-Fine Plus 4mm 32G pen needles that are found to be expired, damaged or defective,
- BD Micro-Fine Plus 4mm 32G pen needles that are possibly the cause of an adverse effect, regardless of whether the product was believed to be damaged, defective or malfunctioning.

The Study Monitor should be contacted with any questions regarding return of study products.

14. Sensitive populations

According to GOST R ISO 14155-2014, a sensitive subject is an individual whose preparedness to participate in the clinical trial can be unduly affected by anticipation, reasonable or not, participation-related benefits or negative reaction of administration in case of his/her refusal to partake. In this study, only *non-sensitive populations* will be enrolled, and all procedures will be carried out under Compulsory Medical Insurance and subsidized pharmaceutical provision. Based on the definition of a sensitive subject, research center staff and Sponsor employees cannot be enrolled in the trial as study subjects.

15. CT suspension or premature termination

Appendix A: Accompanying regulatory documents

«The role of proper insulin injection technique in the treatment of diabetes mellitus»		
Principal investigator:	Name of research center:	Research center number:
ACCOUNTING FORM FOR RECORDING NEEDLE SUPPLY For disposable BD Micro-Fine Plus: 32G (0.23 x 4 mm) needles for injection pen		PAGE ____ OF ____
Dates of needle receipt, number of packages, № and batch	    	Packages ____ Batch № ____
	    	Packages ____ Batch № ____
	    	Packages ____ Batch № ____
	    	Packages ____ Batch № ____
	    	Packages ____ Batch № ____
	    	Packages ____ Batch № ____
Dates of return of unused needles, number of packages, № and batch	    	Packages ____ Batch № ____
	    	Packages ____ Batch № ____
	    	Packages ____ Batch № ____
	    	Packages ____ Batch № ____

Investigator's signature

Date

«The role of proper insulin injection technique in the treatment of diabetes mellitus»				
Principal investigator:	Name of research center:	Research center number:		
ACCOUNTING FORM FOR RECORDING GLUCOMETERS, STRIPS and LANCETS SUPPLY		PAGE ____ OF ____		
Dates of glucometers receipt, number of packages, № and batch	      day	      month	      year	Packages ____ Batch № ____
	      day	      month	      year	Packages ____ Batch № ____
Dates of strips receipt, number of packages, № and batch	      day	      month	      year	Packages ____ Batch № ____
	      day	      month	      year	Packages ____ Batch № ____
Dates of lancets receipt, number of packages, № and batch	      day	      month	      year	Packages ____ Batch № ____
	      day	      month	      year	Packages ____ Batch № ____
Dates of return of unused glucometers, number of packages, № and batch	      day	      month	      year	Packages ____ Batch № ____
Dates of return of unused strips, number of packages, № and batch	      day	      month	      year	Packages ____ Batch № ____
Dates of return of unused lancets, number of packages, № and batch	      day	      month	      year	Packages ____ Batch № ____
Dates of return of USED glucometers, number of packages, № and batch	      day	      month	      year	Packages ____ Batch № ____

Investigator's signature

Date

«The role of proper insulin injection technique in the treatment of diabetes mellitus»

Appendix B: EQ-5D (English and Russian version)

By placing a tick in one box in each group below, please indicate which statements best describe your own health state today.

Mobility

I have no problems in walking about

I have some problems in walking about

I am confined to bed

Self-Care

I have no problems with self-care

I have some problems washing or dressing myself

I am unable to wash or dress myself

Usual Activities (e.g. work, study, housework, family or leisure activities)

I have no problems with performing my usual activities

I have some problems with performing my usual activities

I am unable to perform my usual activities

Pain / Discomfort

I have no pain or discomfort

I have moderate pain or discomfort

I have extreme pain or discomfort

Anxiety / Depression

I am not anxious or depressed

I am moderately anxious or depressed

[figure not shown]
I am extremely anxious or depressed

To help people say how good or bad a health state is, we have drawn a scale (rather like a thermometer) on which the best state you can imagine is marked 100 and the worst state you can imagine is marked 0.

We would like you to indicate on this scale how good or bad your own health is today, in your opinion. Please do this by drawing a line from the box below to whichever point on the scale indicates how good or bad your health state is today.

Your own health state today

Best imaginable health state

Worst imaginable health state

Отметьте галочкой один квадратик в каждом из разделов, приведенных ниже.
Укажите такие ответы, которые наилучшим образом отражают состояние Вашего здоровья на сегодняшний день.

Подвижность

Я не испытываю никаких трудностей при ходьбе

Я испытываю некоторые трудности при ходьбе

Я прикован (-а) к постели

Уход за собой

Я не испытываю никаких трудностей при уходе за собой

Я испытываю некоторые трудности с мытьем или одеванием

Я не в состоянии сам (-а) мыться или одеваться

Привычная повседневная деятельность (например:
работа, учеба, работа по дому, участие в делах семьи,
досуг)

Моя привычная повседневная деятельность дается мне без труда

Моя привычная повседневная деятельность для меня несколько затруднительна

Я не в состоянии заниматься своей привычной повседневной деятельностью

Боль / Дискомфорт

Я не испытываю боли или дискомфорта

Я испытываю умеренную боль или дискомфорт

Я испытываю сильную боль или дискомфорт

Тревога / Депрессия

Я не испытываю тревоги или депрессии

Я испытываю умеренную тревогу или депрессию

[figure not shown]
Я испытываю сильную тревогу или депрессию

Для того, чтобы помочь опрашиваемым высказать свое мнение о том, насколько плохо или хорошо их состояние здоровья, мы изобразили шкалу, похожую на термометр, на которой наилучшее состояние здоровья, которое Вы можете себе представить, обозначено цифрой 100, а наихудшее состояние, которое Вы можете себе представить, обозначено цифрой 0.

Мы бы хотели, чтобы на этой шкале Вы указали, насколько хорошим или плохим по Вашему мнению является состояние Вашего здоровья на сегодняшний день. Для этого Вы должны провести линию от квадрата внизу до той точки на шкале, которая соответствует состоянию Вашего здоровья на сегодняшний день.

Состояние
Вашего здоровья
на сегодняшний
день

Наилучшее
состояние
здоровья, которое
можно себе
представить

Наихудшее
состояние
здоровья, которое
можно себе
представить

1.1 Background and Rationale

Insulin is the drug used in the treatment of diabetes mellitus, and it is administered via injection into subcutaneous adipose tissue. Proper technique of insulin injection in diabetic patients is a prerequisite for achieving good glycemic control, a reduction in the variability of insulin absorption, and reaching optimal efficacy of the anti-diabetic drugs.

To date, several clinical trials have been conducted with the aim of evaluating the effect of proper insulin injection technique on such parameters as glycemic control, glycated hemoglobin, hypoglycemia, glycemic variability and TDD of insulin. These studies attest to the fact that the use of proper injection technique yields tangible results, namely, a reduction in percentage of glycated hemoglobin, an improved control of blood glucose level and an overall improvement of patient satisfaction with treatment. A 6-month follow-up is considered a necessary and sufficient measure for the evaluation of the above parameters. In our study, we would also like to evaluate all the above mentioned parameters with regard to proper injection technique; in addition, physicians' explanations on the injection technique will be reinforced by on-line video lessons, which will be recommended by the attending physician to patients for their own viewing.

1.2 Objectives

1.2.1 Primary Objectives

- Evaluation of the effect of personalized teaching of the optimal insulin injection technique in conjunction with the use of disposable BD Micro-Fine Plus 32G (0.23mm/32G x 4 mm) pen needles on the reduction in glycated hemoglobin (HbA1c in %) after 6 months follow up in patients with Type 1 or Type 2 diabetes .

1.2.2 Secondary Objectives

- Evaluation of the effect of optimal insulin injection technique on the total daily dose of insulin and clinical parameters of glycemic control (hypoglycemia and severe hypoglycemia requiring third party assistance).
- Evaluation of the effect of optimal insulin injection technique on glucose blood levels (measured by BGM).

1.2.3 Additional Objectives

- Evaluation of the effect of education (especially distanced learning) on patients' knowledge and their mastering insulin injection technique, including correctly alternating the injection sites, avoiding injecting the lipohypertrophy areas, and the single use of needles.

2 Study Description

This clinical trial is a prospective, post-marketing, single-arm, multiple-center clinical trial.

2.1 Study Design

A total of 90 patients will be enrolled. Each center will be offered to supply a sufficient number of patients as study subjects (up to 15 patients). Approximately half of these patients will be with lipohypertrophy (LH), and half will be without. Ideally, each center should recruit half of their patients with and half of their patients without LH. The Sponsor will monitor if the overall balance of 50%/50% is maintained and will advise study centers accordingly. The main goal is to have an equal distribution across the study, not necessarily per site, however, each study center should have at least a distribution of 1/3 versus 2/3 in each group. The optimal injection technique and choice of needle length is based on the Russian Procedural Guidelines on injection techniques and infusions used in the treatment of diabetes mellitus. These Guidelines, in turn, are based on recently published international guidelines by the Forum for Injection Technique Therapy Expert Recommendations (FITTER).

2.2 Study Population

The selection of patients will not be influenced by race, religion, socio-economic and other factors. Approximately 50% of the subjects to be enrolled will have lipohypertrophy areas and 50% of the subjects will not.

Inclusion criteria:

- Type 1 or type 2 diabetes mellitus;
- Patients (male and female) of 18 years of age and over;
- At least 1 year of experience with insulin self-administration;
- Use of insulin pen for insulin injections;
- HbA1c > 7.5% measured at study entry or maximally 30 days prior to study entry;
- BMI below 40 kg/m² at study entry;
- Daily self-control of blood glucose level;
- Access to the internet for watching video lessons;
- Only outpatients are eligible for the study;
- Availability of the patient's signed informed consent for inclusion in the study.

Exclusion criteria:

- Pregnant women or women planning to become pregnant during the time of study, breastfeeding women;
- Subjects using an insulin pump;
- Those using treatment with a GLP-1 receptor agonists alone;
- Subjects not fluent in Russian (reading and writing);
- Patients at high risk for ketoacidosis and/or hyperglycemia;
- Psychic, physical or any other reasons hampering patient participation in the study (based on the reasonable opinion of the physician-investigator).

2.3 Sample Size

Based on data observed in internal studies with similar designs, assuming an HbA1c decrease of 0.4% between baseline and 6 months and a standard deviation of paired differences of 1.2%, a sample size of 73 subjects would be needed to demonstrate statistical significance using a one sample t-test with a power

of 80% and alpha equal to 0.05. With a 20% buffer, the sample size needed is 90.

2.4 Study Procedure

The study design and calendar of events, including all the necessary visits, their order, appointment time and manipulations carried out during the visits, are presented in Figure 2.4.1.

[figure not shown]

Figure 2.4.1: Study Flow

2.5 Endpoints

2.5.1 Primary Endpoints

Reduction in glycated hemoglobin (HbA1c in %) after 6 months follow up in patients with Type 1 or Type 2 diabetes.

2.5.2 Secondary Endpoints

- Change in total daily dose of insulin and clinical parameters of glycemic control (hypoglycemia and severe hypoglycemia requiring third party assistance) after 6 months follow up in patients with Type 1 or Type 2 diabetes.
- Change in glucose blood levels (measured by BGM) after 6 months follow up in patients with Type 1 or Type 2 diabetes.

2.5.3 Exploratory Endpoints

- Patients' knowledge and their mastering insulin injection technique, including correctly alternating the injection sites, avoiding injecting the lipohypertrophy areas, and the single use of needles.

- Change of lipohypertrophy, its size (length and width in mm) and localization (if applicable);
- Patients' quantitative experience with the use of distant video lessons

2.6 Acceptance Criteria

There is no acceptance criteria for this study.

3 Intended Statistical Software and Data Information

3.1 Intended Statistical Software

This document was generated with R version 4.0.2 (2020-06-22) [1] and the following packages (version) were used: assertthat (0.2.1), backports (1.2.0), base (4.0.2), BD basics (0.3.3), broom (0.7.3), cellranger (1.1.0), cli (2.2.0), colorspace (2.0.0), compiler (4.0.2), crayon (1.3.4), datasets (4.0.2), DBI (1.1.0), dplyr (2.0.0), dplyr (1.0.2), ellipsis (0.3.1), fansi (0.4.1),forcats (0.5.0), fs (1.5.0), generics (0.1.0), ggplot2 (3.3.2), glue (1.4.2), graphics (4.0.2), grDevices (4.0.2), grid (4.0.2), gtable (0.3.0), haven (2.3.1), hms (0.5.3), httr (1.4.2), jsonlite (1.7.2), lifecycle (0.2.0), lubridate (1.7.9.2), magrittr (2.0.1), methods (4.0.2), modelr (0.1.8), munsell (0.5.0), pillar (1.4.7), pkgconfig (2.0.3), plyr (1.8.6), purrr (0.3.4), R6 (2.5.0), Rcpp (1.0.5), readr (1.4.0), readxl (1.3.1), reprex (0.3.0), rlang (0.4.9), rstudioapi (0.13), rvest (0.3.6), scales (1.1.1), stats (4.0.2), stringi (1.5.3), stringr (1.4.0), tibble (3.0.4), tidyverse (1.1.2), tidyselect (1.1.0), tidyverse (1.3.0), tools (4.0.2), vctrs (0.3.5), withr (2.3.0), xml2 (1.3.2), xtable (1.8.4).

The study analysis will be conducted within the same environment or more recent versions.

4 Analysis Population Set(s)

- Intent-to-treat (ITT) population: All subjects who have been enrolled in this study.
- Per-Protocol (PP) population: The ITT population without any major protocol deviations. A major protocol deviation is defined as a subject not meeting the inclusion/exclusion criteria.

The primary analysis population is the ITT population. Additional analyses on the PP population may be done post-hoc per team's request.

5 Statistical Analysis/Calculations

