7.1. Standards for the clinical trial

To allow for 73 evaluable subjects at 6 months follow up, a total of up to 90 patients will be enrolled (the statistical power of the study is provided in a section below, dedicated to statistical analysis). Each center will be offered to supply a sufficient number of patients as study subjects (up to 15 patients). Approximately half of these patients will be with lipohypertrophy (LH), and half will be without. Ideally, each center should recruit half of their patients with and half of their patients without LH. The Sponsor will monitor if the overall balance of 50%/50% is maintained

and will advise study centers accordingly. The main goal is to have an equal distribution across the study, not necessarily per site, however, each study center should have at least a distribution of 1/3 versus 2/3 in each group. The optimal injection technique and choice of needle length is based on the Russian Procedural Guidelines on injection techniques and infusions used in the treatment of diabetes mellitus [1]. These Guidelines, in turn, are based on recently published international guidelines by the Forum for Injection Technique Therapy Expert Recommendations (FITTER) [5].

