7.4. Patient information and obtaining informed consent

Before executing any study procedure, the informed consent of the patient must be obtained. The following steps must be taken in order to obtain the informed consent of the patient for participation in the study.

1. Physician-investigator must ascertain whether patients understand and read Russian.
2. Patient receives information about the study, its objectives, a brief description of the study design and the patient requirements in case he/she consents to participate in the study. Patients are informed that they meet the criteria required for study entry.
3. Patient takes his/her time to ask questions, discuss the study with family members and take a decision about study participation before the next visit to the medical center. If the patient gives his/her consent to participate in the study, the next visit is scheduled within 5 days from the moment of signing the informed consent form by the patient.
4. Patients are informed that they are entitled to change their mind and withdraw from participation at any time, and this will not affect their treatment in any way.

A patient is considered to be enrolled in the study when he/she signed the Informed Consent Form.

7.5. Stages of the clinical trial.

The enrolment period of the trial will be approximately 1 month, The follow-up period for each patient is 6 months. A total of maximally 90 patients will be included in the trial, to allow for 73 evaluable subjects at 6 months follow up, which is due to the statistical calculation of the required number of patients (see section 10 of this protocol).

The study design and calendar of events, including all the necessary visits, their order, appointment time and manipulations carried out during the visits, are presented in Fig. 2 (Study Flow) Table 1 (Study design) and Table 2 (Calendar of events).

[figure not shown]

Fig. 2. Study Flow

Table 1. Trial design

Patient selection and start		Interim control (telephone)	Interim control (3 month FU visit)	Completion and evaluation
Visit 1 (Screening) duration - 5 working days	1 Patient evaluation in terms of his/her possible participation in the study. For female patients: perform a pregnancy test	1 Make sure that patient follows study protocol: uses supplied needles only once, and watches recommended video lessons	1 Enter data regarding HbA1c and insulin TDD	1 Enter data regarding HbA1c and insulin TDD

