5.2.2 HbA1c

For HbA1c, analysis will be performed using linear mixed effect models to evaluate the effect of personalized teaching of the optimal insulin injection technique in conjunction with the use of disposable BD Micro-Fine Plus 32G pen needles on the response. In the model, subject will be a random effect, time period (baseline, 3 months or end of study) and lipohypertrophy will be fixed effects. Two-way and three-way interactions between fixed effects will be investigated. Only significant interactions will be included in the model. Models will be used to compute estimated mean, difference between baseline and end of study, and corresponding two-sided 95% CI for responses of interest.

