5.2.9 General Considerations

- Missing Insulin or Glycemic data might be imputed, as described in section 5.2.10.
- Imputation might be used during questionnaire analysis if questionnaire pre-process tools contain an imputation routine.
- p-values less than 0.05 will be considered statistically significant. Multiple comparisons adjustments will be made when adequate.
- For each model above, in case the model fails to converge for discrete responses, the random subject effect may be dropped from the model and the average difference between time periods may be calculated across all subjects.
- Initially, two-way interaction will be included into the model. However, if the interaction is not significant (p-value ≥ 0.05), it will be removed from the final model.
- Main effect and interaction plots may be used to graphically show significant effects for each model.
- Residual plots for each model will be drawn and reviewed to ensure there are no systematic patterns. Transformation of response and/or explanatory variables will be investigated whenever modelling assumptions are not satisfied.

- For analysis on discrete responses, a modeling approach will be attempted first and in cases where there are insufficient occurrences for model convergence or a stable model, difference in proportions between categories will be provided and non-parametric testing may be used if modeling assumptions, with or without data transformation, are not satisfied.

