5.2.10 Approaches and Analyses for Missing Data and Other Data Issues

5.2.10.1 Glycaemic Data

Glycaemic data will only be included for analysis if 70% of the expected data is available, i.e. at least ten days over each 14 days period with at least one BGM measure.

Missing glycaemia data will be imputed using median value computed per period per subject when data is not available for a given day only if the data meet the availability of 70% of the expected data requirement.

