5.2.10.2 Insulin Data

Insulin data will only be included for analysis if 70% of the expected data is available, i.e. at least ten days over each 14 days period with at least one basal Insulin dose record and at least ten days over each 14 days period with at least one bolus Insulin dose record. In case a patient did not use boluses, only basal requirements will have to be fulfilled. The pattern of basal and bolus doses can be different (e.g. a day with basal information can have no bolus information).

Missing basal and bolus insulin data will be imputed separately, before TDD computation, using median value computed per period per subject when data is not available for a given day only if the data meet the availability of 70% of the expected data criteria.

6 Summary of General Study Data

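### Does the primary HbA1c analysis need a missing-data rule and a sensitivity analysis, given that up to 17 of 90 enrolled patients may have no 6-month value?

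*SAP*

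**What the plan says.** - **Primary set.** SAP section 4 gives it as "Intent-to-treat (ITT) population: All subjects who have been enrolled in this study". Protocol 7.4 fixes the moment of enrolment: "A patient is considered to be enrolled in the study when he/she signed the Informed Consent Form".
- **Numbers.** Protocol 7.1: "To allow for 73 evaluable subjects at 6 months follow up, a total of up to 90 patients will be enrolled". SAP 2.3 reaches the same total: "With a 20% buffer, the sample size needed is 90". Neither document defines evaluable or says what the buffer is meant to cover.
- **Missing data.** SAP 5.2.9 says "Missing Insulin or Glycemic data might be imputed, as described in section 5.2.10". Section 5.2.10 has two parts. The glycaemic part requires "at least ten days over each 14 days period with at least one BGM measure". The insulin part says "Missing basal and bolus insulin data will be imputed separately, before TDD computation". Neither can apply to a single laboratory HbA1c result per visit.
- **Primary model.** SAP 5.2.2 fits a linear mixed model with subject as a random effect, and with time period (baseline, 3 months, end of study) and lipohypertrophy as fixed effects. On output it says: "Models will be used to compute estimated mean, difference between baseline and end of study, and corresponding two-sided 95% CI". It does not mention patients who lack a later value.
- **Other set.** The per-protocol set in SAP section 4 removes only patients who fail the entry criteria. Its use is optional and post hoc.

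**The concern.** The secondary endpoints have explicit availability thresholds and imputation rules, while the primary endpoint has none. That looks like an oversight.

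The stakes are plain in a single-arm before-after study. No control arm exists in which the same pattern of drop-out could cancel. The intervention depends on patients' own effort, so it is plausible, though nothing in the documents shows it, that those who leave benefit less. If so, a change reported for all enrolled patients would be too large and its confidence interval would sit too far from zero. The per-protocol set cannot reveal this, because it does not separate drop-outs from completers.

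**Working it through.** **Inputs.** Expected fall 0.4 and SD of paired differences 1.2 (Protocol 10.1, SAP 2.3); 73 evaluable and up to 90 enrolled (Protocol 7.1). The documents say nothing about outcomes in patients without a 6-month value, so their mean change d is an assumption and is shown over a range.

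**The plan's own figures.** A two-sided one-sample t-test at alpha 0.05 with effect 0.4 and SD 1.2 needs n = 73 (power 80.2%), as stated. A 20% buffer gives 73 x 1.2 = 87.6 or 73 / 0.8 = 91.25; the stated 90 lies between. The allowance is 90 - 73 = 17, or 17/90 = 18.9%.

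**True all-enrolled change with 17 missing.** Change = (73 x -0.40 + 17 x d) / 90.

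| Mean change d in the 17 | All-enrolled change |
|---|---|
| -0.4 | -0.40 |
| -0.2 | -0.36 |
| 0 | -0.32 |
| +0.2 | -0.29 |
| +0.4 | -0.25 |

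With fewer missing and d = 0: 10 missing gives 80 x -0.40 / 90 = -0.36; 5 missing gives 85 x -0.40 / 90 = -0.38. For the all-enrolled change to be zero, the 17 would have to rise by 73 x 0.40 / 17 = 1.72 points on average.

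**What the SAP 5.2.2 model would report.** Take residual variance 1.2^2 / 2 = 0.72, a common correlation between visits, completers already at -0.40 by 3 months, and d = 0.

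- If the 17 have a baseline value only, the expected estimate is -0.40. The overstatement is 0.40 - 0.32 = 0.08.
- If all 17 also have a 3-month value showing no change, the estimate is -0.378, -0.372 or -0.369 for an assumed HbA1c SD of 1.1, 1.3 or 1.5. The overstatement is about 0.05.

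In simulation of the baseline-only case, the model's 95% CI covered the all-enrolled change 91.7% of the time.

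**Does significance turn on this?** It depends on the variance used. For 73 pairs the SE is 1.2 / sqrt(73) = 0.140 and the 95% CI is -0.68 to -0.12. Now impute a mean change of zero for 17 baseline-only patients:

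- With Rubin's variance the SE is 0.141 and the CI is -0.61 to -0.04. About 65% of trials are significant at the planned effect. The upper limit reaches zero once the imputed mean is +0.21.
- With the SE held at 0.140, that point is +0.24.
- The imputed estimate is 73/90 times the completers' mean, so its repeated-sampling SE is 73/90 x 0.140 = 0.114. The CI is then -0.55 to -0.10. The test statistic equals the completers' own, so about 80% of trials stay significant. The upper limit reaches zero at (0.324 - 1.993 x 0.114) x 90/17 = about +0.52.

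A simulation of the imputation agreed: empirical SE 0.115 against an average Rubin SE of 0.142. The apparent loss of significance comes largely from the variance convention. With fewer missing, the Rubin tipping point moves to +0.71 (10 missing) or +1.78 (5 missing).

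**The case for a change.** The strongest case for a change runs as follows. Missing at random is nowhere written down and nothing tests it. Three-month values repair the bias only in part, and only for patients who have them. A supportive analysis chosen after single-arm data have been seen carries less weight than one fixed beforehand, and writing one in would cost a short subsection. All of that is true.

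Three points limit its force.

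- **Seventeen is a ceiling.** The Protocol synopsis gives a range of 73 to 90 participants.
- **Some of the 17 may never enter follow-up.** Protocol 7.4 requires consent before any study procedure, and the Visit 1 narrative in Protocol 7.5 places the eligibility examination and the HbA1c check after consent. Yet Protocol Table 1 lists patient evaluation first, and 7.4 has patients told during the consent process that they qualify. The share of post-consent screen failures is therefore unknown. Such patients are not drop-outs whose leaving says anything about benefit.
- **Much of the description is already planned.** SAP 6.1 counts patients completing each visit, SAP 5.2.1 summarises every endpoint, and Protocol 7.5 has an exit form completed at the final visit. Only a tabulation of reasons for missing HbA1c would be new.

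**Conclusion.** The omission is real, but it is a gap that analysts fill sensibly, so no change to the plan follows. A likelihood-based mixed model on all observed HbA1c values is a sound primary analysis for three scheduled measurements, and no rule in the SAP is shown to give a wrong result. Adding text would record an assumption the model already makes. A sensitivity analysis would bring in settings, such as the imputed mean and the variance method, that the documents give no basis for choosing.

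At the plan's own inputs, the overstatement is about 0.08 HbA1c points if all 17 are baseline-only and unchanged, and about 0.05 if they all have 3-month values. It shrinks with fewer missing and vanishes if the missing patients changed like the rest. In every scenario up to a rise of 0.4 in the 17, the all-enrolled change is still a fall of at least 0.25. A significant result would then correctly indicate a fall, though its size would be somewhat overstated. SAP 2.6 attaches no decision to that size.

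This rests on reading evaluable as having a 6-month HbA1c, on the planned effect and SD, and on the assumed range of outcomes in the missing patients. A loss well beyond 17, or a much larger rise in those who left, would weaken it.
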